**Table 4 Pharmacokinetic Parameters**

Parameter	Description	Parent	Metabolites	TRA
$C_{\max}$	Maximum observed plasma concentration	X	X	X
$t_{\max}$	Time to attain maximum observed plasma concentration	X	X	X
$AUC_{0-t}$	Area under the plasma concentration-time curve up to time $t$ , where $t$ is the last point with concentrations above the LLOQ	X	X	X
$AUC_{\text{inf}}$	Area under the plasma concentration-time curve from time 0 to infinity calculated as: $AUC_{0-\text{inf}}=AUC_{0-t}+C_{\text{last}}/k_{\text{el}}$ , where $C_{\text{last}}$ is the last measurable plasma concentration	X	X	X
$K_{\text{el}}$	Terminal elimination rate constant	X	X	X
$t_{1/2}$	Terminal elimination half-life, calculated as $0.693/k_{\text{el}}$	X	X	X
$CL/F$	Apparent oral clearance, calculated as dose/ $AUC_{0-\text{inf}}$	X		
$V_z/F$	Apparent volume of distribution at terminal phase	X		
$CL_R$	Renal clearance	X		
$Ae_{\text{urine}}$	Cumulative amount of drug excreted in urine	X	X	X
$Ae_{\text{feces}}$	Cumulative amount of drug excreted in feces			X
$Ae_{\text{vomit}}$	Cumulative amount of drug excreted in vomit, if produced			X
$Ae_{\text{total}}$	Total amount of drug excreted, calculated as $Ae_{\text{total}}=Ae_{\text{urine}}+Ae_{\text{feces}}(+Ae_{\text{vomit}})$			X
$fe_{\text{urine}}$	Fraction of the dose administered excreted in urine (%)	X	X	X
$fe_{\text{feces}}$	Fraction of the dose administered excreted in feces (%)			X
$fe_{\text{vomit}}$	Fraction of the dose administered excreted in vomit (%)			X
$fe_{\text{total}}$	Fraction of the dose administered excreted in urine, feces, and vomit (if produced) (%)			X

TRA=total radioactivity; LLOQ=lower limit of quantification

### 3.5.3.2 Safety Variables

The safety variables to be measured include, but are not limited to, the variables as given below. A complete list of safety variables will be provided in the SAP.

- AEs
- Clinical laboratory
- Vital signs
- 12-lead ECG
- Physical examination

### 3.5.3.3 Exploratory Variables

Metabolite profiling and metabolite identification will be conducted under a separate protocol/bioanalytical study plan, by Nuvisan Grafing, and the results will be reported separately. ~~The metabolite profiling/identification report will be included in the clinical study report (CSR) as an appendix, and results from the metabolite profiling/identification report will be briefly summarized in the CSR.~~

### 3.5.4 Drug Concentration Measurements

The analysis of BTZ-043 and main metabolites in plasma and urine samples will be performed at the Bioanalytical Department of Nuvisan Grafing using validated/qualified LC-MS. The analysis of whole blood, plasma, urine, and feces (and vomit, if produced) for total radioactivity will be conducted at the Bioanalytical Laboratory of PRA using a validated liquid scintillation counting method. The bioanalytical reports for the determinations will be included as appendices in the CSR.

The analysis of quick counts will be conducted at the Bioanalytical Laboratory of PRA using a validated method.

Metabolite profiling in plasma, urine, and feces samples by radiometry will be conducted at the PK Sciences & Biotransformation Department of Nuvisan Grafing. ~~The bioanalytical report for the metabolite profiling and identification will be included as appendix in the CSR.~~

### 3.5.5 Retention of Blood, Plasma, Urine, and Feces Samples

Blood and urine samples remaining after clinical laboratory assessments have been performed will not be stored for future use and will be destroyed after analysis as per laboratory procedure.

Blood, plasma, urine, and feces (and vomit, if applicable) samples remaining after total radioactivity measurements and after sample aliquotation for bioanalytical and metabolite identification have been performed, will be stored at the site of the Promotor and destroyed no later than 10 years after the date of the final CSR.

## 3.6 Statistical Procedures and Determination of Sample Size

### 3.6.1 Analysis Sets

#### 3.6.1.1 Safety Set

All subjects who have received the single oral dose of C-BTZ-043.

#### 3.6.1.2 Pharmacokinetic Set

All subjects who have received the single oral dose of C-BTZ-043 and provided sufficient bioanalytical assessment results to calculate reliable estimates of the PK parameters.

### 3.6.2 Statistical and Analytical Plan for Pharmacokinetic, Safety, and Exploratory Evaluation

A safety SAP will be generated by the Biostatistics Department of PRA and a PK SAP will be generated by Nuvisan; the SAPs will be finalized prior to database lock. Full details of the analysis to be performed will be included in the SAPs.

Any deviation from the SAPs will be reported in the section “Changes in Planned Analysis” in the CSR.

#### 3.6.2.1 Pharmacokinetic Evaluation

The PK parameters and their statistical evaluation of BTZ-043 and main metabolites will be reported as ~~an integrated PK report, which will be included as an appendix and briefly summarized in the CSR. part of the bioanalytical report (included as appendix in the CSR). The PK parameters and their statistical evaluation of total radioactivity will be part of the mass balance report (included as an appendix in the CSR). A separate integrated PK report will incorporate the BTZ-043 and main metabolites' PK, the total radioactivity PK, and the metabolite profiling PK data for an integrated evaluation.~~

All data will be summarized using descriptive statistics and will be listed and summarized in tabular and/or graphical form.

#### 3.6.2.2 Evaluation of Safety and Tolerability

Safety and tolerability will be assessed through AEs, clinical laboratory, vital signs, ECGs, physical examination findings, and any other parameter that is relevant for safety assessment.

##### 3.6.2.2.1 Adverse Events

A listing of all individual AEs will be provided. Summary tables of TEAEs will be presented by system organ class based on the MedDRA terminology list (preferred terms): 1 containing the number of TEAEs (frequency of occurrence, number of subjects experiencing the event) by treatment and 1 containing the number of drug-related TEAEs (frequency of occurrence, number of subjects experiencing the event) per treatment. Additional tables of total counts by treatment and relationship and by treatment and severity will be given.

### 3.6.2.2.2 Clinical Laboratory

Clinical laboratory data will be listed accompanied by an indication if the parameter is outside the reference range. A summary of all data outside the reference range of the clinical laboratory will be provided. Clinical laboratory data will be presented descriptively, where applicable.

### 3.6.2.2.3 Vital Signs and Electrocardiograms

Vital signs and ECG parameters will be listed and they will be presented descriptively, where applicable.

### 3.6.2.2.4 Physical Examination

Changes from baseline for physical examination will be described and listed.

### 3.6.2.3 Evaluation of Exploratory Variables

The PK parameters and their statistical evaluation of metabolites not measured for the primary objectives will be reported in the a separate integrated PK report, which will be included as an appendix and briefly summarized in the CSR.

All data will be summarized using descriptive statistics and will be listed and summarized in tabular and/or graphical form.

The metabolite profiling and identification results will be reported separately (see Section 3.5.4).

### 3.6.3 Determination of Sample Size

Since the present study is a descriptive study aimed at assessing excretion routes of BTZ-043 by evaluating mass balance, a formal statistical sample size calculation was not performed. A sample size of 4 subjects is a minimum accepted number of subjects for AME studies and is considered sufficient to achieve the study objectives. Early-termination subjects may be replaced if the total number of completers drops below 4, after mutual agreement between the Sponsor and PRA.

## 3.7 Data Quality Assurance

The study may be audited by the Quality Assurance Department at PRA to assess adherence to the clinical study protocol (CSP) and Quality System. During the conduct of the study, process-related audits may be performed. An audit certificate will be provided in the appendices of the final CSR outlining any audits and other related activities performed.

The clinical research site will be monitored by the study monitor to ensure correct performance of the study procedures and assure that the study is conducted according to the relevant regulatory requirements. The eCRF entries will be verified with the source documentation, if applicable (in some cases data are captured directly on the eCRF, therefore source data verification is not necessary).

Regulatory authorities, the Independent Ethics Committee (IEC), and/or the Sponsor's clinical quality assurance group may request access to all source documents, eCRFs, and other study documentation for on-site audit or inspection. Direct access to these documents must be guaranteed by the Investigator, who must provide support at all times for these activities.

Quality control principles will be applied throughout the performance of this study. Review procedures will be followed at PRA for all documents that are generated in relation with the study.

An explanation will be given for all missing, unused, and spurious data in the relevant sections of the CSR.

## 4. ETHICS

### 4.1 Independent Ethics Committee

The submission package including the CSP and the ICFs will be submitted for review and approval by the IEC of the foundation “Beoordeling Ethisch Biomedisch Onderzoek” (English translation: “Evaluation of Ethics in Biomedical Research”) ([name] 10, [name], The Netherlands) prior to the eligibility screening. The composition of the IEC is in accordance with the recommendations of the World Health Organization, the International Council for Harmonisation (ICH) E6(R2) Guideline for Good Clinical Practice (GCP) (European Medicines Agency [EMA]/Committee for Medicinal Products for Human Use [CHMP]/ICH/135/1995), and the EU Clinical Trial Directive (CTD) (Directive 2001/20/EC) (see below). The submission package will also be shared with the CA in the Netherlands for a statement of no objection.

PRA will keep the IEC informed about the progress of the study. All changes in research activities and all unanticipated problems involving risks to human subjects will be immediately reported to the IEC. In accordance with Section 10, Subsection 1, of the Dutch law on Medical Research in Human Subjects (WMO, revised Dec 2015), PRA will inform the subjects and the IEC if anything occurs on the basis of which it appears that the disadvantages of participation may be significantly greater than was foreseen in the research proposal, or if further recruitment of subjects in the study has been put on hold for that reason, whichever occurs first. The study may be suspended pending further review by the IEC, except insofar as suspension would jeopardize the subjects' health. PRA will take care that all subjects are kept informed.

No changes will be made to the study without IEC approval, except when required to eliminate apparent immediate hazards to human subjects.

Notification of the end of the study will be sent by PRA to the CA in The Netherlands and to the IEC within 90 days after completion of follow-up for the last subject. In case a study is temporarily halted, PRA will notify the IEC immediately, including the reason for this. In case a study is ended prematurely, PRA will notify the IEC and the CA in The Netherlands within 15 days, including the reasons for the premature termination. A summary of the results of the study will be sent by PRA to the CA and the IEC within 1 year after the end of the study.

The written documentation of approval of the CSP and ICFs will be provided to the Sponsor before the start of the study. Any communication with the IEC and/or CA before, during, and/or after the study will be provided to the Sponsor.

### 4.2 Ethical Conduct of the Study

This study will be conducted in accordance with the ethical principles that have their origin in the World Medical Association (WMA) Declaration of Helsinki, adopted by the 18th WMA General Assembly, Helsinki, Finland, Jun 1964, and subsequent amendments.

This study is also designed to comply with ICH E6(R2) Guideline for GCP (EMA/CHMP/ICH/135/1995), and the EU CTD Directive 2001/20/EC, as incorporated into Dutch Law.

Guidelines adopted by the ICH and other relevant international guidelines, recommendations, and requirements will be taken into account as comprehensively as possible, as long as they do not violate local law.

Whenever the term “Investigator” is noted in the CSP text, it may refer to either the Investigator at the site or an appropriately qualified, trained, and delegated individual of the investigational site.

#### **4.3 Subject Information and Consent**

All subjects will be informed verbally and in writing regarding the objectives, procedures, and risks of study participation. The subjects will be given the time to ask questions. The subjects will have to sign the Dutch or English version of the ICF before any study-related procedures are started. The signed ICFs will be retained and archived at PRA and a copy will be provided to the subject. The ICF contains information about the objectives of the study, the procedures followed during the study, and the risks and restrictions of the study, with special reference to possible side effects of the study drug and potential interactions. In addition, insurance coverage provided during the study is explained. The elements addressed in the ICF are according to the ICH E6(R2) Guideline for GCP (EMA/CHMP/ICH/135/1995).

#### **4.4 Privacy**

All personal details will be treated as confidential by the Investigator and staff at PRA, the Sponsor, and any sub-contractors involved, and handling of personal data will be in compliance with the EU General Data Protection Regulation.

## 5. STUDY ADMINISTRATIVE STRUCTURE

### 5.1 Distribution of Activities

#### 5.1.1 Preparation of Study Drug

The study drug will be prepared at the PRA Pharmacy.

#### 5.1.2 Laboratory Assessments

The analysis of BTZ-043 and main metabolites in plasma and urine samples will be performed at the Bioanalytical Department of Nuvisan Grafing (Grafing, Germany) by using the Nuvisan study protocol G-A-LAB-21-004.

The analysis of total radioactivity in whole blood, plasma, urine, and feces (and vomit, if produced) will be performed at the Bioanalytical Laboratory of PRA (Assen, The Netherlands).

The analysis of clinical laboratory samples will be performed at the PRA Clinical Laboratory.

Metabolite profiling and identification will be performed at the PK Sciences and Biotransformation Department of Nuvisan Pharma Services GmbH (Grafing, Germany) by using the Nuvisan study protocol G-A-MET-21-002.

#### 5.1.3 Electronic Case Report Form Design

The eCRF design will be performed with the computer program Oracle Clinical (Oracle, Redwood Shores, Redwood City, CA, US) by the Database Programming Department of PRA.

#### 5.1.4 Data Management

Data management will be performed with the computer programs Oracle Clinical (Oracle, Redwood Shores, Redwood City, CA, US), SAS® (SAS Institute Inc, Cary, NC, US), and EXACT (Kinship EXACT™, Kinship Technologies, a technology subsidiary of PRA) by the Data Management Department of PRA.

#### 5.1.5 Statistics

A safety SAP will be provided by the Biostatistics Department of PRA. The safety analysis will be conducted by the Biostatistics Department of PRA. Statistical analysis will be performed with the computer program SAS® (SAS Institute Inc, Cary, NC, US). A PK SAP will be provided by Nuvisan Grafing. Statistical evaluation of PK parameters will be conducted by Nuvisan Grafing. PK parameters will be calculated using Phoenix WinNonlin (Pharsight, Mountain View, CA, US). All individual results will be provided to the Sponsor after completion of the study.

#### 5.1.6 Clinical Study Report Writing

The CSR, structured in accordance with the guideline “Structure and Content of Clinical Study Reports - ICH E3”, will be written by PRA and a draft version prepared for

approval by the Sponsor. The final version will be provided as paper version to the Sponsor.

## 5.2 Documentation

### 5.2.1 Archiving

All documents concerning the study will be kept on file in the Central Archives of PRA for at least 25 years after conduct of the study. The Sponsor will receive the completed eCRFs as PDF file.

### 5.2.2 Recording of Data in Source Documents and Electronic Case Report Forms

Wherever possible, all data will be entered directly into the eCRFs. Source documents will be used in some cases.

A data management plan will be written by the Data Management Department of PRA, which will be finalized prior to performing any data validation. An appendix to the data management plan (origin of source data list for data entry) will identify any data to be recorded directly in the eCRF (ie, no prior written or electronic record of data) and which data should be considered source data.

## 6. CONFIDENTIALITY AND PUBLICATION POLICY

All information generated in this study is considered highly confidential and must not be disclosed to any person or entity not directly involved with the study unless prior written consent is gained from the Sponsor and Promotor. However, authorized regulatory officials, the Sponsor and its authorized representatives are allowed full access to the records.

All study subjects must be informed that their personal study-related data will be used by the Sponsor in accordance with local data protection law. The level of disclosure must also be explained to the subject, who will be required to give consent for their data to be used as described in the ICF. The subjects must be informed that their medical records may be examined by auditors or other authorized personnel appointed by the Sponsor, by appropriate IEC members, and by inspectors from regulatory authorities.

Identification of subjects and eCRFs shall be by unique subject numbers only.

All personal details will be treated as confidential by the Investigator and staff at PRA.

All relevant aspects regarding publication will be part of the contract (or similar document) between the Sponsor and PRA.

## 8. APPENDICES

### 8.1 Drug Accountability

Upon receipt of the study drug, it will be inspected and counted by the responsible pharmacist. If necessary, all study drug will be repacked per dosing occasion and labeled according to PRA SOPs.

The study drug will be kept in the PRA Pharmacy or in a locked and secured storage facility accessible to the pharmacist and the pharmacy assistant only. Temperature is monitored 24/7 with an automatic environmental monitoring system. In case of an alarm, the pharmacist or pharmacist on duty is informed immediately by email and phone.

The responsible pharmacist will keep an inventory. This will include a description of the formulation and the quantity of study drug received for the study and a record of what is dispensed, to whom, and when.

On termination of the study, the responsible pharmacist will conduct a final inventory of the study drug supply and will record the results of this inventory in the Drug Accountability Form. Unused study drug will be returned to the Promotor upon notice is given to Promotor and Sponsor or will be locally destroyed according to PRA standard procedures. Final accountability needs to be verified by monitor before return and/or destruction of medication.

### 8.2 Adverse Events and Serious Adverse Events Evaluation and Reporting

#### 8.2.1 Adverse Events

An AE is any unfavorable and unintended sign (including an abnormal laboratory finding), symptom, or disease temporally associated with the use of a medical treatment or procedure that may or may not be considered related to the medical treatment or procedure. AE definitions will be followed as stated in the “Note for Guidance on Clinical Safety Data Management: Definitions and Standards for Expedited Reporting” (ICH topic E2A).

All AEs reported by the subjects or apparent from their physical appearance during the clinical study will be reported on the AE eCRF page.

The severity of AEs will be graded using the most current version of the MedDRA:

- **Mild:** An AE that is easily tolerated by the subject, causes minimal discomfort, does not interfere with everyday activities, and does not require intervention.
- **Moderate:** An AE that is sufficiently discomforting to interfere with normal everyday activities; intervention may be needed.
- **Severe:** An AE that prevents normal everyday activities; treatment or other intervention usually needed.

If an AE has multiple aspects, the aspect with the highest severity will be graded.

It is emphasized that the term severe is a measure of severity; thus, a severe AE is not necessarily serious. For example, itching for several days may be rated as severe, but may not be clinically serious.

In addition, clinically significant changes in physical examination findings and abnormal objective test findings (eg, laboratory, x-ray, ECG) should also be recorded as AEs. Test findings and physical examination findings can result in AEs if they:

- Are associated with accompanying symptoms, and/or
- Require additional diagnostic testing or medical/surgical intervention, and/or
- Lead to a change in study dosing or discontinuation from the study; result in the addition of significant additional concomitant drug treatment or other therapy, and/or
- Lead to any of the outcomes included in the definition of an SAE, and/or
- Are considered to be an AE by the Investigator or Sponsor.

Reporting as an AE should not be triggered by:

- Merely repeating an abnormal test, or
- Any abnormal test result that is determined to be an error.

The relationship of any AE to the study drug will be assessed and graded as related or not related.

**Related:**

- The AE follows a reasonable temporal sequence to study drug administration, and cannot be reasonably explained by the subject's clinical state or other factors (eg, disease under study, concurrent diseases, or concomitant medications).
- The AE follows a reasonable temporal sequence to study drug administration, and is a known reaction to the drug under study or a related chemical group, or is predicted by known pharmacology.

**Not Related:**

The AE does not follow a reasonable sequence from study drug administration, or can be reasonably explained by the subject's clinical state or other factors (eg, disease under study, concurrent diseases, and concomitant medications).

## 8.2.2 Serious Adverse Events

An SAE is any untoward medical occurrence that, on the basis of medical and scientific judgment:

- Results in death, or
- Is life-threatening (this refers to an event in which the patient was at risk of death at the time of the event; it does not refer to an event which hypothetically might have caused death if it were more severe), or
- Requires inpatient hospitalization for a medical reason or prolongation of existing hospitalization (this refers to hospital admission required for treatment of the AE). (Note: this does not include confinement in, for example, a respite unit; a skilled

nursing unit; rehabilitation facility; the clinical research center; or confinement due to planned or unplanned reason unrelated to study), or

- Results in persistent or significant disability/incapacity, or
- Is a congenital anomaly/birth defect.
- Medical and scientific judgment should be exercised in deciding whether expedited reporting is appropriate in other situations, such as important medical events that may not be immediately life-threatening or result in death or hospitalization, but may jeopardize the patient or may require intervention to prevent one of the other outcomes listed in the definition above. These should also usually be considered serious. Examples of such events are intensive treatment in an emergency room or at home for allergic bronchospasm, blood dyscrasias, or convulsions that do not result in hospitalization.

SAEs will be collected from admission until the final study visit. SAEs that are related to the investigational drug and continue beyond the normal collection period (ie, are ongoing at the time a subject exits the study) will be followed until resolution or until stabilized with sequelae. SAEs that begin after the subject's participation in the study is complete, but that the Investigator considers to be related to study drug, may be reported at any time.

The Investigator or clinical site personnel must notify the Sponsor's Medical Monitor and PRA Drug Safety Center of all SAEs, regardless of relationship to the investigational drug, within 24 hours of clinical site personnel becoming aware of the event. The Investigator will provide the initial notification by sending a completed "SAE Notification Form," which must include the Investigator's assessment of the relationship of the event to investigational drug and must be signed by the Investigator.

In addition, notification is sent by PRA to the IEC and the subject's General Practitioner.

Follow-up information, or new information regarding an ongoing SAE, must be provided promptly to the Sponsor's Medical Monitor and PRA Drug Safety Center.

All SAE reports should be sent to the contacts provided on Page 4: SAE Contact Information.

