16.1.2 Deaths and Serious Adverse Events

A listing of deaths and other serious adverse events (SAE) will be provided by subject.

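### The note to the SAE hospitalization criterion can make seriousness depend on relatedness, so an unplanned admission considered unrelated to the study may not be classed as an SAE

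*Protocol*

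**What the plan says.** Protocol Appendix 8.2.2 lists the outcomes that make an untoward event serious. The hospitalization criterion reads "Requires inpatient hospitalization for a medical reason or prolongation of existing hospitalization (this refers to hospital admission required for treatment of the AE". That sentence sets no relatedness condition. A note in the same bullet lists stays that do not count. It names several non-hospital settings and ends "nursing unit; rehabilitation facility; the clinical research center; or confinement due to planned or unplanned reason unrelated to study". The protocol file contains the appendix twice, with the same wording.

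Three other provisions bear on the point:

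- Appendix 8.2.1 defines an adverse event as one "that may or may not be considered related to the medical treatment or procedure".
- Appendix 8.2.2 requires the site to tell the sponsor's medical monitor and the CRO's safety unit about "all SAEs, regardless of relationship to the investigational drug, within 24 hours of clinical site personnel becoming aware of the event". Ethics committee and general practitioner are also told of SAEs.
- SAP Section 16.1.2 says: "A listing of deaths and other serious adverse events (SAE) will be provided by subject". This is Table 15.3.2.1 in SAP Appendix 4. The SAP gives no seriousness definition of its own.

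**The concern.** Seriousness describes the outcome of an event, and relatedness describes its cause. They are normally assessed separately so that a judgement about cause cannot decide whether the event is reported quickly. Excluding planned stays and stays in non-hospital units is ordinary. Excluding an unplanned stay because it is unrelated to the study puts a causal judgement inside the seriousness test.

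The expedited route depends on that classification: the 24-hour notice, the ethics committee notification and the SAE listing all start from events already classed as SAEs. An admission removed by the note would not enter that route, in a study whose secondary objective is safety and tolerability.

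**Working it through.** No arithmetic decides this point, and the plan states no figure to reproduce. The check is to apply the provisions of Appendix 8.2.2 to one case.

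**Case.** A dosed subject has an unplanned hospital admission to treat an adverse event. The event is not fatal, life-threatening or disabling, is not a congenital anomaly, and is not judged an important medical event.

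**Step 1, the criterion.** The first half of the bullet asks only whether admission was required to treat the event. It was, so the event is serious.

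**Step 2, the note.** The note limits the hospitalization criterion, so on its plain meaning confinement in a hospital is within its reach. If the reason is considered unrelated to the study, the note removes the event. A narrower reading is possible: the listed settings are non-hospital units, so the closing words may mean only stays that were not made to treat an adverse event.

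| Same admission, no other criterion met | Note read plainly | Note limited to stays not made to treat an AE |
|---|---|---|
| Considered related to the study | SAE | SAE |
| Considered unrelated to the study | Not an SAE | SAE |

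Under the plain reading the two rows differ in relatedness alone. Under the narrow reading they do not differ. The text does not say which reading applies.

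**Step 3, whether another provision repairs it.**

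- The notification rule covers all SAEs whatever their relationship, but it acts only after an event has been classed as an SAE.
- The important-medical-event clause says of such events "These should also usually be considered serious". It can bring some admissions back in, but by judgement, and it is framed around events that may not lead to hospitalization.
- Section 3.3.3 requires immediate notice when a subject is withdrawn. After a single dose, an admission following discharge need not lead to withdrawal.
- The SAP takes the serious classification as given.

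None of these cancels the exclusion.

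**Step 4, where the event would still appear.** SAP Section 16.1.1 lists every recorded adverse event. If treatment-emergent, the event is also counted by system organ class and preferred term, by relationship and by severity. What changes is the serious flag, the row in Table 15.3.2.1 and the expedited notices.

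**Step 5, exposure to the problem.** Four subjects are dosed, or up to 4 + 2 = 6 with replacements. From discharge on Day 5 to 8 until follow-up on Day 31, each subject is outside the unit for 31 − 8 = 23 to 31 − 5 = 26 days, apart from any return visits and the ±2-day window. The documents give no admission rate.

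**The case against.** The strongest reply is that the note does not mean what it seems to say. The protocol elsewhere uses confinement for the stay in the research unit, as in the Table 1 row of that name, and the other items in the note are non-hospital settings. In addition, *unrelated to study* is not the relationship the protocol grades, which is to the study drug. Both observations are fair. They show that the wording is ambiguous, not that it is safe: the note sits inside the hospitalization criterion, and nothing limits its last item to non-hospital stays.

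The reply also limits the consequences. A reader might infer any of the following, and the documents do not support them:

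- *Every unrelated admission escapes.* Fatal, life-threatening or disabling events remain SAEs, and the important-medical-event clause may capture others.
- *The investigator's drug-relatedness grade alone decides.* The note refers to the study, and that relationship is not defined.
- *The sponsor loses a second causality assessment.* Appendix 8.2 describes only the investigator's assessment. The sponsor also receives the completed eCRFs (Section 5.2.1), so the 24-hour notice may be lost but the information is not.
- *SUSAR reporting is lost.* A SUSAR must be an adverse drug reaction (Appendix 8.2.3), so an event judged unrelated to the drug would not qualify in any case.
- *SAE incidence falls from 1/4 = 25% or 1/6 = 17% to zero.* The SAP plans an SAE listing and no SAE incidence table.
- *COVID-19 is a foreseen example.* Sections 3.2.1 and 3.3.3.1 speak of referral for treatment and quarantine, and do not mention hospital admission.

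**Conclusion.** The note is wrong as written. On its plain reading it makes the hospitalization criterion turn on relatedness, against the first half of the same bullet and against the relationship-free notification rule. On the narrower reading it does not, and a site has no basis in the text for choosing between them.

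The size is small. The defect matters only if there is an unplanned hospital admission to treat an adverse event, the event is considered unrelated to the study, no other seriousness criterion is met, and the note is read plainly. With 4 to 6 dosed subjects that is unlikely. If it happens, one event may miss the 24-hour notice, the ethics committee notification and the SAE listing, while remaining in the adverse event data as non-serious. The primary mass-balance analysis is unaffected. The conclusion rests on the wording alone and on no assumed event rate.

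**What to change.** In Appendix 8.2.2, delete *or unplanned* and *unrelated to study* from the note, so that it excludes only pre-planned stays and stays not made to treat an adverse event. Then add one sentence: *Seriousness is judged independently of relationship to the study drug or study.* Carry the same sentence into the SAE form instructions.

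The SAP needs no change, because its listing follows the protocol's classification. The cost is a short edit to the appendix and the form instructions and, at most, an occasional extra SAE report. The change concerns a reporting definition only and alters no dose, procedure or analysis.
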